7. STATISTICAL ANALYSIS

All statistical analyses and reporting will be performed using the SAS® System Version 9.3 or later.

Unless otherwise specified, continuous variables will be summarized with descriptive statistics (n, mean, median, standard deviation, standard error, minimum, and maximum), and categorical variables will be summarized with counts and percentages.

All data collected in the study database will be presented in the listings.

Definition of Study Eye: The study eye will be the eye that meets the entry intraocular pressure (IOP) criteria after washout. Should both eyes meet the criteria, then the study eye will be defined as the eye with the higher 8 am IOP on Baseline (Day 0). If both eyes have the same 8 am IOP on Baseline (Day 0), the study eye will be the right eye. The study eye will be designated by the investigator. The designation may take into account ocular history as well as IOP criteria.

Definition of Baseline:

For vital signs, PK, BCVA and biomicroscopy baseline is the pre-T0 time point on Day 1. For clinical laboratories and pupil diameter baseline is the Day 0 collection. For IOP and hyperemia baseline is the set of repeated measures at different times during the Day 0 visit. For ophthalmoscopy baseline is the Screening Day.

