3. STUDY ASSESSMENTS/ENDPOINTS

Informed Consent: Properly executed informed consent (written and verbal) is to be obtained prior to completion of any study-related procedures. Subjects must review, sign, and date the informed consent document and receive a copy.

Medical and Ophthalmic History: Relevant and clinically significant medical and ophthalmic history must be recorded.

Concomitant Medications: All prescription and over-the-counter (OTC) medications and nutritional supplements taken during the study and 30 days prior to the Screening Visit will be recorded. Diagnostic eye drops do not need to be recorded.

Randomization: Randomization will be accomplished using an Interactive Web Response System (IWRS). Site personnel will receive instruction about IWRS access and use.

Adverse Events: Any events occurring after the first dose of IP will be recorded as an adverse event. At each visit, the subject should be asked questions such as, "How are you feeling? How are your eyes feeling today? Have you had any changes since the last exam?"

IP Administration and Compliance: The first dose of study IP will be administered to the study eye by study staff after the IOP measurement at T0 + 12 hrs. At Day 1/Visit 3 the AM dose of

study IP will be administered to the study eye by study staff after the IOP measurement at T0. Subjects will self-dose unilaterally until the Day 4 visit. At Day 4/Visit 4 the AM dose of study IP will be administered OU by study staff after the IOP measurement at T0. Subjects will self-dose OU for the remainder of the trial except on Day 14/Visit 5 (AM and PM doses) and Day 28/Visit 6 (AM dose) when study IP will be administered OU by study staff after the related IOP measurements. Compliance will be assessed at applicable visits by asking the subject about any missed doses. If the subject reports missing more than 4 doses since the prior visit, the subject will be counseled on IP compliance.

Heart Rate and Blood Pressure (BP) Measurements: Both systolic and diastolic blood pressure should be recorded.

Heart rate measurements will be measured by radial pulse. The subject should be in a seated and relaxed state. An automated blood pressure unit may be used to measure the heart rate.

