7.7 Ocular and Other Medical History

Ocular and other medical history reported at the Screening Visit and on Day 0 prior to the first dose of study drug, will be summarized by System Organ Class and Preferred Term.

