7.10 Vital Signs

Descriptive statistics of vital signs and their change from baseline will be tabulated by time point and treatment group.

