7.12 Best-Corrected Visual Acuity

Descriptive statistics of the observed and change from baseline BCVA will be tabulated for each eye by visit and treatment group.

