7.13 Ocular Hyperemia, Biomicroscopy, Ophthalmoscopy and Ocular Symptoms

The observations of ocular hyperemia, biomicroscopy, ophthalmoscopy, and ocular symptoms will be summarized in frequency tables based on the ordinal scales for each measure for each eye by time point and treatment group. In addition, the photographic assessment of ocular hyperemia will be summarized by descriptive statistics (See Appendix 2).

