9. APPENDICES

9.1 Appendix 1: Schedule of Study Assessments and Procedures

Assessments/Procedures ¹	Screening (-42 ² to -1 days)	Day 0 Baseline/ Randomization	Day 1	Day 4 (± 1 day)	Day 14 (± 1 day)	Day 28 Exit/ET (± 2 days)
	Visit 1	Visit 2	Visit 3	Visit 4	Visit 5	Visit 6
Informed Consent	X					
Medical and Ophthalmic History	X	X				
Concomitant Medications	X	X	X	X	X	X
Adverse Events		X	X	X	X	X
Randomization		X				
IP Administration in Office		X Unilateral post T ₀ + 12 hrs IOP	X Unilateral post IOP	X OU post IOP	X OU post T ₀ and T ₀ + 12 hrs IOP	X OU post T ₀ IOP (final dose)
Assess IP Compliance				X	X	X
Heart Rate/Blood Pressure (± 30 min)	X	X Pre-T ₀ T ₀ + 1 hr T ₀ + 2 hrs T ₀ + 4 hrs				X Pre-T ₀ T ₀ + 1 hr T ₀ + 2 hrs T ₀ + 4 hrs
ECG	X					
Physical Examination	X					
Best-corrected Visual Acuity (ETDRS)	X	X Pre-T ₀	X Pre-T ₀	X Pre-T ₀	X Pre-T ₀	X Pre-T ₀
Biomicroscopy ³ (± 30 min)	X	X T ₀ T ₀ + 2 hrs T ₀ + 4 hrs T ₀ + 8 hrs T ₀ + 12 hrs	X Pre-T ₀	X Pre-T ₀	X Pre-T ₀	X Pre-T ₀ T ₀ + 2 hrs T ₀ + 4 hrs T ₀ + 8 hrs T ₀ + 12 hrs
Pupillary Diameter (± 30 min)		X Pre-T ₀				X Pre-T ₀

¹ When possible, one examiner should conduct all ocular assessments for a subject during a single visit. If possible, the same examiner should conduct all ocular assessments for a subject throughout the duration of the study.

² +1 week permitted to accommodate scheduling considerations

³ If any adverse findings are noted after IP administration, the subject should continue to be monitored per the investigator's judgment.

Assessments/Procedures ¹	Screening (-42 ² to -1 days)	Day 0 Baseline/ Randomization	Day 1	Day 4 (± 1 day)	Day 14 (± 1 day)	Day 28 Exit/ET (± 2 days)
Conjunctival Hyperemia Grading (± 30 min)		X T ₀ T ₀ + 2 hrs T ₀ + 4 hrs T ₀ + 8 hrs T ₀ + 12 hrs		X Pre-T ₀	X Pre-T ₀	X Pre-T ₀ T ₀ + 2 hrs T ₀ + 4 hrs T ₀ + 8 hrs T ₀ + 12 hrs
Intraocular Pressure ⁴ (Goldmann Tonometry) (± 30 min)	X	X T ₀ T ₀ + 1 hrs T ₀ + 2 hrs T ₀ + 4 hrs T ₀ + 8 hrs T ₀ + 12 hrs	X T ₀	X T ₀	X T ₀ T ₀ + 1 hr T ₀ + 2 hrs T ₀ + 4 hrs T ₀ + 8 hrs T ₀ + 12 hrs	X T ₀ T ₀ + 1 hr T ₀ + 2 hrs T ₀ + 4 hrs T ₀ + 8 hrs T ₀ + 12 hrs
Pachymetry ⁵	X					
Gonioscopy ⁶	X					
Visual Fields (automated, threshold)	X ⁷					
Dilated ophthalmoscopy	X					X ⁸
Blood Collection for PK of H-1337 (± 10 min at 2 & 8 hrs)		X				X Pre-T ₀ T ₀ + 2 hrs T ₀ + 8 hrs
Clinical Laboratories (hematology, clinical chemistry, pregnancy (if applicable), and urinalysis)	X ⁹	X ¹⁰				X ¹¹

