9.2 Appendix 2. Efficacy Endpoints and Time Points

IOP

Category	Day 0 Visit	Day 1 Visit*	Day 4 Visit*	Days 14 & 28 Visits
Eye subgroups	Study eye Mean of both eyes	Study eye	Study eye	Study eye Mean of both eyes
Analysis variables	IOP & Diurnal IOP	
• IOP• Change in IOP from baseline (Day 0 Visit)*• % change in IOP from baseline (Day 0 Visit)*• Proportion of subjects achieving IOP \leq 18 mmHg	
• IOP• Change in IOP from baseline (Day 0 Visit)• % change in IOP from baseline (Day 0 Visit)• Proportion of subjects achieving IOP \leq 18 mmHg	
• IOP & Diurnal IOP• Change in IOP & Diurnal IOP (Day 0 Visit)• % change in IOP & Diurnal IOP (Day 0 Visit)• Proportion of subjects achieving IOP/Diurnal IOP \leq 18 mmHg
Analysis Time points	
• T_0$T_0 + 1$ hrs$T_0 + 2$ hrs$T_0 + 4$ hrs$T_0 + 8$ hrs$T_0 + 12$ hrs• Diurnal (mean of 5 measurements & mean of 4 measurements excluding $T_0 + 12$ hrs)	T_0	T_0	
• T_0$T_0 + 1$ hrs$T_0 + 2$ hrs$T_0 + 4$ hrs$T_0 + 8$ hrs$T_0 + 12$ hrs• Diurnal (mean of 5 measurements & mean of 4 measurements excluding $T_0 + 12$ hrs)
Treatment Groups/ Comparisons	H-1337 vs. Vehicle	H-1337 vs. Vehicle	H-1337 vs. Vehicle	H-1337 vs. Vehicle

*Note: the non-study eye will not be treated until after T_0 on the Day 4 visit. Day 0 measures will be used as baseline for all time points for the non-study eye.

Conjunctival Hyperemia by Photographic Assessment

Category	Day 0 Visit	Day 4 Visit*	Day 14 Visit	Days 28 Visit
Eye subgroups	Study eye Mean of both eyes	Study eye	Study eye	Study eye Mean of both eyes
Analysis variables	Conjunctival Hyperemia by Photographic Assessment	
HyperemiaChange in Hyperemia from baseline (Day 0 Visit)*	
HyperemiaChange in Hyperemia from baseline (Day 0 Visit)	
HyperemiaChange in Hyperemia from baseline (Day 0 Visit)
Analysis Time points	
Pre-T_0$T_0 + 2$ hrs$T_0 + 4$ hrs$T_0 + 8$ hrs$T_0 + 12$ hrs	
Pre-T_0	
Pre-T_0	
Pre-T_0$T_0 + 2$ hrs$T_0 + 4$ hrs$T_0 + 8$ hrs$T_0 + 12$ hrs
Treatment Groups/ Comparisons	H-1337 vs. Vehicle	H-1337 vs. Vehicle	H-1337 vs. Vehicle	H-1337 vs. Vehicle

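### The SAP sets the baseline for vital signs and BCVA after the first dose, on Day 1, when no vital signs are scheduled

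*SAP*

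**What the plan says.** The baseline paragraph in SAP section 7 reads: "For vital signs, PK, BCVA and biomicroscopy baseline is the pre-T0 time point on Day 1". The same paragraph uses Day 0 for laboratories, pupil diameter, IOP and hyperemia, and Screening for ophthalmoscopy.

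SAP section 3 has the first dose "administered to the study eye by study staff after the IOP measurement at T0 + 12 hrs" on Day 0, and Protocol section 5 agrees. SAP 7.7 also puts the first dose on Day 0: it covers history "reported at the Screening Visit and on Day 0 prior to the first dose of study drug". For the fellow eye, the note in SAP Appendix 2 says that "the non-study eye will not be treated until after T_0 on the Day 4 visit".

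Two planned safety tables use this baseline:

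- SAP 7.10: "Descriptive statistics of vital signs and their change from baseline will be tabulated by time point and treatment group".
- SAP 7.12: "Descriptive statistics of the observed and change from baseline BCVA will be tabulated for each eye by visit and treatment group".

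Biomicroscopy has no change table. Under SAP 7.13 the findings "will be summarized in frequency tables based on the ordinal scales for each measure for each eye by time point and treatment group".

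**The concern.** A baseline should come before treatment and should be a value that the trial collects. For vital signs the Day 1 rule meets neither condition. For study-eye BCVA it fails the first.

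The two failures show themselves differently. The vital-sign failure is visible, because the programmer finds no Day 1 record. Someone must then choose between Screening, Day 0 pre-T0 and the time-matched Day 0 readings, and the SAP does not say which. The BCVA failure is silent. A Day 1 pre-T0 record exists, so the table fills normally, but a loss of acuity already present on Day 1 that persisted would be absorbed into the baseline and would not appear in the change column.

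This matters because safety is the primary objective (SAP 2.1) and H-1337 had not been given to humans before (Protocol 1.3). ECG and physical examination are scheduled only at Screening. Heart rate and blood pressure are therefore among the few systemic safety measures scheduled on treatment.

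**Working it through.** No sample-size or power figure is involved. The check sets the baseline rule against the dosing text and the two schedules (Protocol synopsis and SAP Appendix 1), then counts the table cells affected.

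**Time from first dose to the named baseline.** T0 is 8 am ± 30 min (inclusion criteria), so T0 + 12 h on Day 0 is about 20:00.

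- Nominal: (24 + 8) − 20 = 12 h.
- With ± 30 min at each end: from (24 + 7.5) − 20.5 = 11 h to (24 + 8.5) − 19.5 = 13 h.

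The true interval is slightly shorter, because the dose follows the IOP reading and the Day 1 assessment precedes T0.

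**What is scheduled.**

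| Measure | Day 1 reading | Day 0 reading before first dose | Planned change table |
|---|---|---|---|
| Heart rate/BP | none | pre-T0, +1, +2, +4 h | yes (SAP 7.10) |
| BCVA | pre-T0 in SAP Appendix 1; no time given in the protocol schedule | pre-T0 | yes (SAP 7.12) |
| Biomicroscopy | pre-T0 | T0, +2, +4, +8, +12 h | no, frequency tables only |
| PK (selected sites) | none | one sample, any time before dosing | none |

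The procedure list for Days 1 and 4 in Protocol 5.1.3 also contains no heart rate or blood pressure.

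**Could Day 1 be another numbering convention?** No. The same paragraph uses Day 0 for other measures, SAP 7.7 places the first dose on Day 0, and both schedules head the Day 0 column as Baseline and show Day 1 as a separate visit.

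**Vital signs.** The Day 28 change summaries number 4 time points x 3 parameters (heart rate, systolic, diastolic) x 4 arms = 48. With no scheduled Day 1 readings, 0 of 48 can be computed.

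**BCVA, study eye.**

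- Day 1 baseline: 3 later visits (Days 4, 14, 28) x 4 arms = 12 change summaries, all starting from a post-dose value.
- Day 0 baseline: 4 later visits (Days 1, 4, 14, 28) x 4 arms = 16.
- Lost: 16 − 12 = 4, the Day 1 summaries, where change is zero by definition.

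At nominal visit days the study eye receives 1 (Day 0) + 27 x 2 (Days 1–27) + 1 (Day 28) = 56 doses, of which 1 precedes the Day 1 baseline.

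**BCVA, fellow eye.** It is undosed until Day 4, so its Day 1 value still precedes local dosing.

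**Biomicroscopy and PK.** No planned change table is affected. The named reference point is post-dose for study-eye biomicroscopy and unscheduled for PK.

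**The case against.** The strongest reply is that Day 1 is a one-character slip for Day 0. Day 0 is called Baseline throughout, vital signs and BCVA both have a pre-T0 reading that day, and a programmer would meet the vital-sign problem at once. The tables are descriptive. Observed BCVA is tabulated by visit and all data are listed, so an early change would still be visible there. Adverse events are collected from Day 0, and Protocol section 5 asks the investigator to look into a BCVA change of 10 letters or more, whatever the SAP baseline. Nothing in the documents suggests that a single drop alters acuity at 12 hours.

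Most of this stands, and it limits the consequence. The counts above show how much of the tables is affected. They do not estimate bias in letters or mmHg, and the documents give no basis for such an estimate.

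It does not remove the defect. The sentence is the SAP's only baseline rule for these measures, and for BCVA it matches a real scheduled reading, so nothing prompts a correction. Changing 1 to 0 is also not quite enough: Day 0 biomicroscopy starts at T0, so a pre-T0 reading does not exist for it and the reading must be named.

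On the procedure lists, Protocol 5.1 refers to the schedule for what is done, so the omission of heart rate and blood pressure from the Day 0 list in 5.1.2 is secondary. It is still worth reconciling, because a corrected baseline depends on those readings. Similarly, 5.1.4 lists them under Days 14 and 28 without limiting them to Day 28, while the schedule has none on Day 14.

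**Conclusion.** The concern holds. As written, the vital-sign change table cannot be produced (0 of 48 summaries). The study-eye BCVA change table starts about 12 hours (11 to 13) after the first dose in all 12 of its summaries and omits the 4 that Day 1 would give. This assumes that visits follow the schedule at nominal days and that the SAP sentence is applied literally.

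No hypothesis test is affected, and neither is the fellow-eye BCVA value as a pre-dosing reference. The rule does not touch laboratories, pupil diameter, IOP, hyperemia or ophthalmoscopy. Day 1 is probably a slip, but it governs tables that serve the primary objective and should be corrected before database lock and unmasking. Choosing the baseline afterwards would make it a post hoc decision.

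**What to change.** Replace the sentence in SAP section 7 so that baseline is a named Day 0 assessment before the first dose:

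- vital signs and BCVA: Day 0 pre-T0;
- biomicroscopy: Day 0 T0 (other Day 0 readings also precede dosing, but one must be named);
- PK: the Day 0 pre-dose sample.

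Treat Day 1 BCVA and biomicroscopy in the study eye as post-dose results. Reconcile the Day 0 list in Protocol 5.1.2 with the schedule so that the four heart rate/blood pressure readings are clearly required. Optionally, add change from the time-matched Day 0 vital-sign readings as a further summary.

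The cost is one SAP sentence, the related programming and a clarification of the protocol list. No assessment is needed beyond those already scheduled.

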7.1 Subject Disposition

Subject disposition, including the number of subjects randomized, treated, and completing the study (and completing each study visit), will be tabulated by treatment group. The percentage of subjects treated and completing the study will be based on the total number randomized.

Eligibility criteria exemptions and major protocol deviations will be summarized by treatment group and presented in a listing. Major protocol deviations may include the following: violation of inclusion or exclusion criteria, using prohibited medications, non-adherence to study treatment schedule.

The total number and percentage of subjects included in each of the analysis datasets described in Section 5 will be summarized by treatment group, with percentages based on the total number randomized subjects.

Discontinuations and the reasons for discontinuation will be summarized for all randomized subjects. Summaries will include the number and percentage of subjects within each treatment group. Reasons for discontinuation following the receipt of study drug will include the following:

1. Protocol violation
2. Lost to follow-up
3. Adverse event
4. Non-compliance
5. Subject withdrew consent
6. Investigator decision
7. Uncontrolled IOP
8. Other

7.2 Demographic and Baseline Characteristics

The demographic and baseline characteristics will be summarized for all randomized subjects by treatment group.

Continuous variables such as age will be summarized using descriptive statistics (n, mean, standard deviation, median, minimum, and maximum), and categorical variables such as gender, race, and ethnicity will be summarized using counts and percentages of subjects.

Age will be determined as the whole integer number of years from the date of birth (DOB) to the date of the screening visit, i.e., the truncated integer difference between the DOB and Visit 1.

Baseline comparability between treatment groups will be assessed via descriptive statistics.

Prior medications will be tabulated by preferred term (WHO drug dictionary).

Medical and surgical history classified using MedDRA dictionary will be presented in a listing.

7.3 Treatment Compliance and Exposure

The number of subjects by number of doses missed will be summarized by eye, visit and treatment group.

Duration of drug exposure will be calculated for each subject as the number of days they received any study drug. The number and percentage of subjects by treatment group will be summarized according to the following duration-of-exposure categories: ‘<7 days’, ‘7 to <14 days’, ‘14 to <21 days’, ‘21 to <31 days’, and ‘≥31 days’.

7.4 Intraocular pressure

The comparisons among treatment groups in IOP will be done for the various endpoints and time points. The outline of the analyses and groups is presented in Appendix 2.

For each visit in which IOP is measured descriptive statistics at each time point will be presented for the observed, change from baseline and % change from baseline values. In addition, at visits where five assessments are made descriptive statistics will be presented for the average of the observed values and the change from baseline and percent change from baseline where the values will be computed using average of five corresponding values at Day 0 as a baseline.

Descriptive statistics of IOP measures described above will be presented for the study eye, non-study eye and average of both eyes by time point and treatment group.

The 95% confidence intervals of the mean IOP by treatment group and time point and for diurnal IOP as well as for corresponding change from baseline will be presented.

For the IOP, diurnal IOP, and their change from baseline, each of the active treatment groups will be compared to the placebo group using the analysis of covariance (ANCOVA) model, separately for each time point. Baseline value will be used as a covariate. The difference between treatment groups in adjusted least-square means will be presented. Mean diurnal IOP will be presented as the mean of all values (including the 8 pm IOP value) (12-hour diurnal) and mean of all values up to the 4 pm IOP value (8 hour diurnal). If a subject is missing any time point for the calculation of the diurnal IOP, that subject will be excluded from the affected diurnal IOP analysis in the per protocol population.

The proportion of subjects reaching a target IOP (≤ 18 mmHg) at each time point and with the mean diurnal IOP for each visit will be presented by treatment group.

Within each dose level the change from baseline IOP will also be compared (a within subject comparison) with descriptive statistics.

Exploratory summaries may be presented to examine if treatment effects differ depending on iris color, age and baseline IOP.

Each comparison will be tested at the significance level of 0.05. No adjustments for multiple comparisons will be made.

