6 ASSESSMENT OF EFFICACY

6.1 Efficacy Parameters

Primary Efficacy Endpoints:

The primary efficacy measure will be the mean change in IOP from Baseline (Day 0) IOP (mmHg) for each group on Days 14 and 28 at each matched time point as compared to vehicle. IOP will be measured according to the Schedule of Assessments and Procedures Table.

Secondary efficacy endpoints:

1. The observed IOP, mean change from Baseline, and % change from Baseline IOP at each matched time point at each visit, and
2. The mean observed, mean change from Baseline and mean % change from Baseline for the mean diurnal IOP at each visit, and
3. The proportion of subjects reaching a target IOP (≤ 18 mmHg) at each time point and with the mean diurnal IOP for each visit. Each concentration will be compared to vehicle and the difference in means between treatment arms will be presented.

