8 STATISTICAL PLAN

8.1 Sample Size

The sample size is driven by interest in the IOP lowering effect of H-1337. The study is designed to test whether one or more concentrations of H-1337 are superior to the vehicle control in the reduction of IOP. With $n = 20/\text{group}$ this stage is powered at 94% to detect a difference in IOP reduction of 4.0 mmHg between groups against a standard deviation of 3.5 mmHg (2-sided t-test, alpha=0.05).

Adverse events: With 20 subjects per group there is a 95% certainty that an event that is not observed would have a true incidence rate of no more than 15%.

Hyperemia: Scored on a 5-point scale from 0 to 3. Assume the SD is 20% of the scale range or 1 unit. Then, with $n = 20/\text{group}$ there is 86% power to detect a mean difference of 1 unit between pairs of groups (2 group two-sided t-test, alpha=0.05). If a response is defined as a hyperemia score ≥ 3 and the response rate in the control group is 10%, then with $n = 20/\text{group}$ there is 85% power to detect a difference in response rates of 46% (Fisher's exact test).

In general, with 20 subjects per group there is 86% power to detect an effect size of 1.0.

If a concentration is chosen that is less than the maximum, the safety data from the higher doses can be combined to increase power.

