2.4 Randomization

Randomization will be stratified by Baseline IOP (23 to 26 mmHg and > 26 to 32 mmHg at 8 am). H-1337 and its vehicle will be packaged in identical bottles. An interactive web response system (IWRS) will be used for randomization.

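### The IOP ANCOVA leaves out the 8 am IOP randomization stratum, so standard errors at the later time points may be slightly too large

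*SAP*

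**What the plan says.** SAP 2.4 (and Protocol 3.2) fixes the design: "Randomization will be stratified by Baseline IOP (23 to 26 mmHg and > 26 to 32 mmHg at 8 am". The strata start at 23 mmHg, the entry threshold for the study eye, so I read the stratifier as study-eye IOP.

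SAP 7.4 compares each concentration with vehicle "using the analysis of covariance (ANCOVA) model, separately for each time point". The only adjustment it names is "Baseline value will be used as a covariate". The stratum appears in no model. Baseline IOP comes back only as one of the factors for optional exploratory summaries.

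SAP 7.4 does not say which baseline value is meant. Three other statements point to the time-matched one:

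- SAP 7, Definition of Baseline: "For IOP and hyperemia baseline is the set of repeated measures at different times during the Day 0 visit".
- Protocol 6.1 defines the primary efficacy measure as change from Day 0 "for each group on Days 14 and 28 at each matched time point as compared to vehicle".
- For diurnal IOP, SAP 7.4 computes change "using average of five corresponding values at Day 0 as a baseline".

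The time-matched reading is therefore an inference, but a well-supported one.

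**The concern.** Stratified allocation balances the arms on the stratifier and so removes its contribution from the treatment contrast. If the model then omits the stratifier, its variance stays in the residual. The model reports more uncertainty than the design leaves, intervals are somewhat wide, and tests are somewhat conservative.

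A continuous baseline covariate usually deals with this, and at 8 am it does, because the covariate is the stratification variable itself in continuous form. At T0 + 1, 2, 4, 8 and 12 hours the covariate is a different reading, which carries the stratum only as far as it correlates with 8 am IOP. What is at stake is a little precision in dose-versus-vehicle comparisons with 20 subjects per arm, not validity.

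**Working it through.** **Inputs from the documents.** 20 per arm in four arms; difference 4.0 mmHg and SD 3.5 mmHg (Protocol 8.1, SAP 4); "2-sided t-test, alpha=0.05"; "Each comparison will be tested at the significance level of 0.05", without multiplicity adjustment (SAP 7.4); six IOP times on Days 0, 14 and 28. Not given: correlations between IOP readings, block size, and the share of subjects in each stratum.

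**1. The plan's own figure.** SE = 3.5 × √(2/20) = 1.107 mmHg; noncentrality 4.0/1.107 = 3.61 on 38 df; power 94.1% (95.1% by normal approximation). The stated 94% is reproduced. It describes an unadjusted t-test, so neither baseline nor stratum enters it.

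**2. How many comparisons are affected.** Primary comparisons: 3 concentrations × 6 times × 2 visits = 36. At T0: 3 × 1 × 2 = 6. After T0: 3 × 5 × 2 = 30.

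Diurnal baselines average in the 8 am reading. With k readings and a common correlation ρ, the correlation of one reading with their mean is √[(1 + (k − 1)ρ)/k]. For k = 6 this is √(3/6) = 0.71 at ρ = 0.4 and √(4/6) = 0.82 at ρ = 0.6, so most of the stratum information is already in the model.

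**3. Size by formula.** Let r be the partial correlation of the stratum with follow-up IOP, given treatment and time-matched baseline. The SE without the stratum divided by the SE with it is about 1/√(1 − r²). Taking 3.5 mmHg as the residual SD of the SAP's model (an assumption):

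| r (assumed) | SE ratio | SE with stratum, mmHg | Power for 4.0 mmHg |
|---|---|---|---|
| 0 | 1.000 | 1.107 | 94.1% |
| 0.1 | 1.005 | 1.101 | 94.3% |
| 0.2 | 1.021 | 1.084 | 94.9% |
| 0.3 | 1.048 | 1.056 | 95.8% |
| 0.4 | 1.091 | 1.014 | 97.0% |

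**4. Size by simulation.** Assumptions: four arms of 20, 8 am IOP limited to 23–32 mmHg, blocks of four within stratum, SD 3.5 mmHg, no treatment effect, one four-arm model, 8,000 runs per row. Monte Carlo error is about 0.8% on the reported/true ratio and 0.25 points on type I error. B0 is 8 am baseline, Bt the time-matched baseline, Y the follow-up reading.

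| Correlations B0–Bt, B0–Y, Bt–Y | r | Reported/true SE, SAP model | Type I error, SAP model | Reported SE without and with stratum |
|---|---|---|---|---|
| 0.6, 0.36, 0.6 | 0.00 | 0.998 | 4.8% | 0.889, 0.889 |
| 0.6, 0.3, 0.5 | 0.00 | 0.994 | 5.3% | 0.961, 0.963 |
| 0.7, 0.5, 0.6 | 0.09 | 1.003 | 5.2% | 0.884, 0.882 |
| 0.6, 0.5, 0.5 | 0.18 | 1.006 | 5.0% | 0.945, 0.930 |
| 0.5, 0.5, 0.5 | 0.20 | 1.009 | 4.6% | 0.937, 0.917 |
| 0.4, 0.6, 0.5 | 0.32 | 1.041 | 3.7% | 0.900, 0.853 |

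In the last row the true SD of the estimate is 0.865 without the stratum and 0.860 with it, nearly the same. The design has already removed the stratum from the contrast; adding the term mainly lets the model report that.

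A further run, with all three correlations equal at 0.6 and at 0.7, gave reported/true ratios of 1.018 and 1.024. The reported SEs were 0.862 against 0.837, and 0.768 against 0.741, without and with the stratum.

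**5. Power for a smaller effect.** With an assumed residual SD of 3.0 mmHg and a 3 mmHg effect, slopes of 0.6 on 8 am IOP and 0.4 on the matched reading (correlation 0.4) give 83.8% without the stratum and 85.9% with it. Equal slopes of 0.4 give 85.8% and 86.4%. When 8 am IOP adds little there is no gain and no measurable loss. For diurnal IOP, a separate run with slopes 0.6 and 0.4 and pairwise correlation 0.6 gave 83.3% and 83.6%.

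**The case against.** A reader might infer that standard errors after 8 am are too large as a matter of fact, and that the plan loses power through it. The documents do not support that. It needs balanced allocation within strata, for which no block size is given, and it needs 8 am IOP to predict follow-up IOP beyond the time-matched reading, for which no correlation is given. If the second condition fails there is no inflation, as the first two simulation rows show. The largest effects come from letting 8 am on Day 0 predict a later clock time better than that clock time's own Day 0 reading does, and nothing in the documents supports this. This part of the objection stands and limits the claim to a possibility.

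A reader might also extend the point to diurnal IOP as if its baseline excluded the stratifier. It does not: the 8 am reading is part of the mean, and step 5 shows almost no gain.

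It is also fair that safety is the primary objective, that Protocol 8.5 describes a small exploratory trial, and that any error is on the conservative side. These arguments lower the priority; they do not remove the omission. The zero-gain case is a special one, since it requires one noisy Day 0 reading to hold everything the 8 am reading says about follow-up. If both are noisy readings of the same underlying pressure, the second adds information.

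**Conclusion.** The omission is confirmed and its consequence is minor. The stratification factor is in no IOP model, and for 30 of the 36 primary comparisons the named covariate, read as time-matched, is not the variable used to stratify. At those times the reported standard error may exceed the true one by 0 to about 4%, and the stratum-adjusted one by 0 to about 6%. Both ranges rest on assumed correlations and on balanced allocation within strata. At 8 am little is lost, and for diurnal means the gap is small.

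Treatment estimates stay unbiased. Type I error is not inflated; in the strongest scenario it falls to 3.7%. The stated 94% power stands, because it was computed for an unadjusted comparison. I am confident of the omission and of the direction of any effect, but not of its size.

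**What to change.** In SAP 7.4:

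- State that the ANCOVA covariate is the Day 0 value at the same clock time or, for diurnal IOP, the matching Day 0 diurnal mean.
- Add the randomization stratum (8 am Day 0 study-eye IOP, 23 to 26 versus above 26 to 32 mmHg) as a fixed effect in the study-eye IOP ANCOVAs.

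Restrict the second change to the study eye. Appendix 2 also lists analyses of the mean of both eyes, for which a study-eye stratum is a less obvious match.

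The cost is a sentence or two and one degree of freedom: one of 80 − 5 = 75 residual df if a single four-arm model is fitted, or one of 40 − 3 = 37 if each concentration is compared with vehicle in its own model. If 8 am IOP adds nothing, the reported standard error is essentially unchanged. No new data are needed, and the change can be prespecified because the SAP is to be finalized before database lock and unmasking.
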